## **8.2 Radiation Toxicities**

8.2.1 Radiation therapy side effects are typically divided into acute, those that occur acutely (during radiation and up to three months after radiation), and late (greater than three months post-radiation) toxicities. Common acute radiation side effects include fatigue, skin irritation or erythema, nausea, emesis, acid-reflux symptoms, diarrhea, and hematologic depressions. Typically, these side effects are mild and can be controlled with medications. Late side-effects that are unlikely to occur may include permanent sterility or infertility, peptic ulcer disease, change in bowel patterns, small or large bowel obstruction, biliary stricture, liver damage, and decreased renal functioning. Another rare but serious late side effect is the development of secondary tumors. It is hoped that proton radiation therapy will substantially reduce both acute and late side effects by reducing the amount of normal tissue that is irradiated.

8.2.2 Acute and late radiation effects will be defined according to section according to section 7.1.2. Acute radiation toxicity will be scored up to 90 days from initiation of radiation therapy, for which CTCAE 4.0 (Appendix A) will be employed. Late radiation effects will be scored beyond 90 days from the start of radiation therapy at timepoints delineated according to the follow up schedule outlined in section 6.2.1 and will also be evaluated using CTCAE 4.0 (Appendix A).

## **8.3 Assessing and Recording Adverse Events**

All Adverse Events and Serious Adverse Events will be assessed using NCI Common Terminology Criteria for Adverse Events Version 4.0 (CTCAE 4.0) [Appendix A].

## **8.4 Reporting of Serious Adverse Events**

Adverse Event Reporting Period: the study period during which Adverse Events must be collected and Serious Adverse Events must be reported is normally defined as the period from the initiation of any study procedures to the end of the study treatment follow-up (off study at progression). This protocol will begin assessment of AEs and SAEs following the first treatment fraction of radiation therapy. Therefore, only treatment emergent events will be evaluated.

## **8.5 Institutional Review Board (IRB) Notification by Investigator**

All events meeting the Penn IRB Standard Operative Procedure for Unanticipated Events posing risks to subjects or others will be reported to the IRB as follows:

### **Unanticipated problems are:**

(1) Unforeseen; and (2) indicate that participants are at increased risk of harm. The IRB requires investigators to submit reports of the following problems within 10 working days **with one exception:** an Adverse Event (regardless of whether the event is serious or non-serious, on-site or off-site) that occurs any time during or after

the research study, which in the opinion of the Principal Investigator is both unexpected and related to research procedures.

Note: An event is “unexpected” when its specificity and severity are not accurately reflected in the protocol-related documents, such as the IRB-approved research protocol, any applicable investigator brochure, and the current IRB-approved informed consent document, and (b) other relevant sources of information, such as product labeling and package inserts; an event is “related to the research procedures” if the event is deemed probably or definitely related.

The **one exception** for prompt reporting within 10 days applies to death of a research participant. If the adverse event involved death as unforeseen and indicates participants or others are at increased risk of harm, a submitted report will be required within three working days.

#### **8.5.1 MGH/DOD Reporting**

It is the responsibility of the participating investigator to notify the Principal Investigator and the local IRB of all SAEs. The participating investigator must report each SAE the Principal Investigator within 24 hours of learning of the occurrence. The participating center will report the event to the coordinating center at: [name] [contact] or [contact]. Within 24-28 hours, the participating investigator must provide follow-up information on the SAE which shall include if the issue has been resolved or is continuing, treatment that was given and whether the subject will continue with participation. MGH and DOD will submit all appropriate correspondence regarding SAEs to their respective IRBs.

All non-serious adverse events will be reported to the Principal Investigator via the toxicity care report forms. Further reporting details can be found in the accompanying manual of operating procedures.

#### **8.6 Data and Safety Monitoring Committee (DSMC) Notification by Investigator**

Any expected, unrelated event that is a Grade 3 or higher should be reported to the DSMC within 10 days. All unexpected deaths or deaths related to the study agent or device need to be reported to the DSMC within 24 hours. All other AEs should be reported within 30 days of knowledge.

Any SAEs, regardless of site, are to be reported to the Principal Investigator within 24 hours via telephone or email. For SAEs that occur at MGH and DOD, the site will submit documentation to their IRB according to their regulations in addition to submitting documentation to the Coordinating Center who will then submit to the IRB (as required) and to the DSMC in the manner specified above.

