#### **8.7 Safety Event Notification of Enrolling Sites**

The lead institution will maintain documentation of all adverse event reporting and will be responsible for communicating all serious adverse events to all participating sites. The Principal Investigator is responsible for distributing all safety reports to all participating institutions for their review and subsequent submission to their IRB if required.

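### Section 8.6 gives non-fatal Grade 3+ events that are related or unexpected a slower DSMC limit (30 days) than those that are expected and unrelated (10 days)

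*Combined protocol and SAP*

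**What the plan says.** Section 8.6 sorts events into three classes for the DSMC:

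- The 10-day class is defined by two conditions that must both hold: "Any expected, unrelated event that is a Grade 3 or higher should be reported to the DSMC within 10 days".
- The 24-hour class is for any death that was not foreseen or that is attributed to the treatment under study.
- The residual class, with the longest limit, takes whatever the first two leave over: "All other AEs should be reported within 30 days of knowledge".

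The second paragraph of 8.6 sends serious adverse events (SAEs) to the Principal Investigator within 24 hours. For onward reporting to the DSMC it refers back to the classes above and adds no clock of its own.

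Section 8.5, on unanticipated problems, sets the IRB deadline: "The IRB requires investigators to submit reports of the following problems within 10 working days". It applies to an adverse event, serious or not, "which in the opinion of the Principal Investigator is both unexpected and related to research procedures". An event counts as related "if the event is deemed probably or definitely related". An unforeseen death that indicates increased risk has a shorter IRB limit of three working days.

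**The concern.** A safety committee most needs to hear early about severe events that may be caused by the treatment or that nobody foresaw. For non-fatal events, 8.6 does the reverse. Its 10-day sentence covers only events that are both expected and unrelated, which say least about proton therapy. The related and the unexpected ones are not named anywhere in 8.6, so they drop into the residual 30-day class.

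At stake is the speed of independent oversight. Several other notification routes depend on the event being serious, and CTC grade is not seriousness. A related Grade 3 toxicity that meets none of the criteria in 8.1.2, for example because it needs no hospital stay, is outside the SAE routes. Section 8.6 is then its only event-level DSMC deadline.

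**Working it through.** No figure in the plan needs reproducing. The check applies the three sentences of 8.6 to every combination of outcome, expectedness and relatedness for a Grade 3+ event, now and under the proposed fix.

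| Grade 3+ event | Limit in 8.6 now | Limit after the fix |
|---|---|---|
| Non-fatal, expected, unrelated | 10 days | 10 days |
| Non-fatal, expected, related | 30 days | 10 days |
| Non-fatal, unexpected, unrelated | 30 days | 10 days |
| Non-fatal, unexpected, related | 30 days | 10 days |
| Death, expected, unrelated | 10 days | 10 days |
| Death, expected, related | 24 hours | 24 hours |
| Death, unexpected, unrelated | 24 hours | 24 hours |
| Death, unexpected, related | 24 hours | 24 hours |

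**Size.** Among non-fatal events, 3 of 4 combinations have the longer limit. The ratio is 30 / 10 = 3 and the difference is 30 − 10 = 20 days, if both are calendar days, which 8.6 does not state. These are outer limits, not expected delays.

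**Sign of a slip.** For deaths, 8.6 puts unexpected or related cases first. Section 8.5 also gives priority to events that are unexpected and related. Only the non-fatal Grade 3+ rows run the other way.

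**Comparison with the IRB limit.** Only the unexpected and related row has an 8.5 deadline. Ten working days are two working weeks, so at most 14 calendar days without a public holiday. The 30-day DSMC limit is later. The other two affected rows have no 8.5 deadline to compare with.

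**Search for another DSMC deadline.** Each other clock was checked for its recipient and trigger:

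- Sections 8.5.1 and 8.6: SAEs go to the Principal Investigator within 24 hours. Participating investigators must also act "to notify the Principal Investigator and the local IRB of all SAEs". Neither recipient is the DSMC.
- Section 8.7: the lead institution "will be responsible for communicating all serious adverse events to all participating sites". This informs sites and has no DSMC clock.
- Section 6: clinicians confer within 5 business days of a grade 3 toxicity, and monthly teleconferences cover current toxicities. Neither reaches the DSMC.
- Section 3.7: adverse events and SAEs are entered in Velos within two weeks. This is data entry, not a report to the DSMC.
- Section 9.1.2: a Medical Monitor report that requires action goes to the DSMC within 10 business days. The monitor sees all adverse events, serious or not, so this route does not depend on seriousness. It is triggered by a report requiring action, not by an individual event, and the scheduled meetings are quarterly.
- Section 9.2.1: the DSMC reviews SAEs, deviations and monitoring reports monthly. This is a review cycle, not a reporting deadline.

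None of these sets an event-level DSMC deadline for the three affected rows.

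**The case against.** The strongest reply is that this is an evident wording error with little practical effect. Staff would probably report a related severe toxicity promptly. The Principal Investigator hears of SAEs within a day, the IRB hears of unexpected and related events within 10 working days, and the Medical Monitor can trigger a report to the DSMC. The committee meets monthly, so a report 20 days earlier need not be reviewed 20 days earlier. The manual of operating procedures (8.5.1) and the institutional monitoring plan (9.2.1) may set stricter clocks.

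Much of this stands. A slip is the likely explanation, oversight exists through several routes, and the real delay cannot be estimated from the documents. What does not stand is the inference that the text can be left alone. An investigator who reports a related Grade 3 toxicity to the DSMC on day 30 complies with 8.6, more than one site works from it, and the documents do not say that another order was meant. If the manual or the monitoring plan is stricter, the protocol should agree with it.

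A reader might also infer that 8.5 and 8.6 contradict each other. They do not: both limits are maximums and an investigator can meet both. The fault is the ordering inside 8.6.

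**Conclusion.** The point holds as a defect of wording in an operative safety-reporting rule. For three of the four combinations of non-fatal Grade 3+ event, the DSMC limit is 30 days instead of 10, and those are the more informative combinations. This rests on a literal reading of 8.6 and on the supplied documents alone.

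Three stronger readings are tempting and are not supported:

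- That the most informative severe events in general have the slowest limit. Related or unexpected deaths have the fastest one, 24 hours.
- That the early-termination rule in 7.1.3 is compromised. It counts patients treated and followed for 90 days, and nothing in the documents makes that count depend on the DSMC reporting clock. No effect on the endpoint or the analysis is shown either.
- That a number of affected patients can be given. The 20% in 7.1.3 is a limit of acceptability for acute non-hematologic toxicity, whereas 8.6 covers all Grade 3+ events, and the documents do not give the share that would be related or unexpected.

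The change should be made because it is cheap and the current order serves no stated purpose.

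**What to change.** Reword 8.6 as follows:

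- Keep the 24-hour limit for unexpected or related deaths.
- Apply the existing 10-day limit to all other Grade 3 or higher events, whatever their expectedness or relatedness. The words should not be restricted to non-fatal events: that would drop expected, unrelated deaths from 10 days into the 30-day class.
- Set the DSMC deadline for any unexpected and related event no later than the IRB deadline in 8.5. Once Grade 3+ events are at 10 days, this clause matters mainly for lower-grade events, since 8.5 applies to non-serious events too.
- Leave the remaining adverse events at 30 days.
- State whether days are calendar or working, and that each clock starts at knowledge of the event. At present only the 30-day sentence gives a starting point.

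Check the result against the manual of operating procedures and the institutional monitoring plan. The cost is one or two sentences and slightly faster paperwork for a few events. Design, sample size and analysis are untouched.

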#### **8.7 Safety Event Notification of Enrolling Sites**

The lead institution will maintain documentation of all adverse event reporting and will be responsible for communicating all serious adverse events to all participating sites. The Principal Investigator is responsible for distributing all safety reports to all participating institutions for their review and subsequent submission to their IRB if required.

## 9 Medical Monitoring

### 9.1 Medical Monitor

- 9.1.1 It is the responsibility of the Principal Investigator to oversee the safety of the study at his/her site. This safety monitoring will include careful assessment and appropriate reporting of adverse events as noted above, as well as the construction and implementation of a site data and safety-monitoring plan (see protocol section 12). Medical monitoring will include a regular assessment of the number and type of serious adverse events.
- 9.1.2 The Medical Monitor (MM) will be [name]. Because of [name]'s background and experience in the treatment of patients with seminoma, he is an appropriate MM for this study. In this role, he will be given a report to review that will include all AEs, including grading, toxicity assignments, dose modifications, appropriateness of dose escalation, and all other safety data and activity data observed in the ongoing clinical trial, along with discussing relevant animal and toxicology studies and similar investigational agents. The MM may recommend reporting of adverse events and relevant safety data not previously reported and may recommend suspension or termination of the trial. The Principal Investigator and the study coordinator will meet with the MM quarterly (or as needed) in person or via email. The MM will receive the report of the study's progress one week before the meeting. This report will include information from MGH, DOD and UPENN sites. Serious and unexpected issues will be handled on an ad hoc basis through calls or e-mail. Documentation of MM activity will be maintained in the study specific Regulatory Binder. Copies of an MM report requiring action on the part of the Principal Investigator to protect subject safety or study integrity must be submitted to the DSMC within 10 business days. Meetings that are held between the Medical Monitor and the PI will be recorded by the study coordinator.

### 9.2 Abramson Cancer Center's Internal Data and Safety Monitoring

#### 9.2.1 Data and Safety Monitoring Committee

- The Abramson Cancer Center DSMC is charged with the responsibility of reviewing all SAEs, deviations, and Medical/Safety Monitoring reports for all cancer-based protocols conducted at the University of Pennsylvania. The DSMC reviews these document and data on a monthly basis and makes recommendation necessary to ensure subject safety and study integrity. The Department of Compliance and Monitoring (DOCM) will monitor and audit the progress and conduct of all cancer-based studies in accordance with their National Cancer Institute-approved Institutional Data and Safety Monitoring Plan.

#### 9.2.2 Protocol Deviations/Exceptions

Occasionally, the investigator may need to deviate from the approved protocol. Deviations are categorized as reportable and non-reportable. Reportable deviations may be urgent or not. Urgent deviations may occur on the spot as necessary to protect the safety of a study subject and do not allow enough time for reporting in advance. However, they must be reported as soon as possible.

A one time, **intentional** action or process that departs from the IRB and CTSRMC approved study protocol, intended for **one** occurrence. If the action disrupts the study progress, such that

the study design or outcome (endpoints) may be compromised, or the action compromises the safety and welfare of study subjects, **advance** documented IRB and DSMC approval is required. A one time, **unintentional** action or process that departs from the IRB and DSMC approved study protocol, involving one incident and **identified retrospectively**, after the event occurred. If the impact on the protocol disrupts the study design, may affect the outcome (endpoints) or compromises the safety and welfare of the subjects, the deviation must be reported to the DSMC within 5 business days and the IRB within 10 business days.

- All deviations from the study protocol will be handled as follows:
  - **Eligibility** - Exceptions from established eligibility criteria will not be allowed. If the investigator believes that an ineligible subject would truly benefit from the protocol therapy and there are no other viable alternatives, then the protocol should be amended to reflect the change in restrictions. There may be situations where the exception from eligibility may not warrant a study amendment (e.g. a necessary test/procedure being a few days outside of the eligibility window, a subject taking a concomitant medication within a recent timeframe, etc.). These exceptions must still be reviewed and approved in advance of enrolling the subject. The IRB must be notified of the planned exception, and a copy of all applicable amended study documents must be sent to the IRB. The planned deviation must also be submitted to the DSMC for evaluation. **Other Reportable** - Deviations that affect the protocol treatment administration (i.e. dose administered, route/method of administration, etc.), dose adjustment schema, stopping rules, modification to follow-up, removal of safety assessments/follow-up visits, accrual goal, or any deviation that may affect the study outcome analysis or study integrity must be approved by the IRB and reviewed by the DSMC.
  - **Non-Reportable** - During the course of a study, there may be times when deviations are outside of the control of the investigator (i.e. a subject not showing up for a study visit, laboratory errors, subject confusion, etc.). These types of deviations are not reportable (unless they occur at a level that impacts any of the reportable categories), but they must be documented in a timely manner to show the impact of the deviation and corrective/follow-up actions that are being taken. Documentation can be in clinic/progress notes or in notes/memos to file. Notes/memos should be signed and dated.
  - **Reporting Deviations/Exceptions** - Reports to the IRB and DSMC will be done via the DSMC website at [www.ctsrmc.org](http://www.ctsrmc.org). Reportable deviations must also be sent to the study MM (if applicable). Please reference above section.

## 10 Data Handling and Record Keeping

### 10.1 Confidentiality

- 10.1.1 Information about study subjects will be kept confidential and managed according to the requirements of the Health Insurance Portability and Accountability Act of 1996 (HIPAA). Those regulations require a signed subject authorization informing the subject of the following:
- What protected health information (PHI) will be collected from subject(s) in this study.
  - Who will have access to that information and why.
  - Who will use or disclose that information.

- The rights of a research subject to revoke their authorization for use of their PHI.
- 10.1.2 In the event that a subject revokes authorization to collect or use PHI, the investigator, by regulation, retains the ability to use all information collected prior to the revocation of subject authorization. For subjects that have revoked authorization to collect or use PHI, attempts should be made to obtain permission to collect at least vital status (i.e. that the subject is alive) at the end of their scheduled study period.

## **10.2 Unintentional Disclosure:**

Upon discovering that PHI may have been or has been disclosed to anyone not specified in the HIPAA disclosure consent, the investigator will report the disclosure to the Institutional Officer in the Office of Research Compliance and Integrity. The report should contain details about the type of data disclosed and the extent of the disclosure (number of subjects, who received it, etc.).

## **11 Study Monitoring, Auditing, and Inspecting**

11.1 The study Principal Investigator is responsible for ensuring the ongoing quality and integrity of the research study. In addition, this study will be monitored or audited in accordance with Abramson Cancer Center's National Cancer Institute-approved Institutional Data and Safety Monitoring Plan.

11.2 Auditing and Inspecting: the Principal Investigator will permit study-related monitoring, audits, and inspections by the IRB, government regulatory bodies, and University compliance and quality assurance groups of all study-related documents (e.g. source documents, regulatory documents, data collection instruments, study data, etc.). The Principal Investigator will ensure the capability for inspections of applicable study-related facilities (e.g. pharmacy, diagnostic laboratory, etc.).

11.3 Participation as an investigator in this study implies acceptance of potential inspection by government regulatory authorities and applicable University compliance and quality assurance offices.

## **12 Ethical Considerations**

This study is to be conducted according to United States and international standards of Good Clinical Practice (FDA Title 21 part 312 and International Conference on Harmonization guidelines), applicable government regulations, and Institutional research policies and procedures.

This protocol and any amendments will be submitted to a properly constituted IRB, in agreement with local legal prescriptions, for formal approval of the study conduct. The decision of the IRB concerning the conduct of the study will be made in writing to the Principal Investigator and a copy of this decision will be maintained in the study specific Regulatory Binder which contains "Essential Study Documents." In addition, the National Cancer Institute requires all cancer-based studies to have an independent scientific review. This protocol must be reviewed and fully approved by the Clinical Trials Scientific Review and Monitoring Committee (CTSRMC)

prior to enrolling any subjects. Documentation of CTSRMC approval must also be maintained in the study specific Regulatory Binder.

All subjects for this study will be provided a consent form describing this study and providing sufficient information for subjects to make an informed decision about their participation in this study. See Appendix G for a copy of the Subject Informed Consent Form. This consent form will be submitted with the protocol for review and approval by the IRB and CTSRMC for the study. The formal consent of a subject, using the IRB-approved consent form, must be obtained before that subject is submitted to any study procedure. This consent form must be signed and dated by the subject or legally acceptable surrogate, and the investigator-designated research professional obtaining the consent.

